5.2 Trial Treatments

The treatment to be used in this trial is outlined below in Table 2

Table 2 Trial Treatment

Drug	Dose/Potency	Dose Frequency	Route of Administration	Regimen/Treatment Period		
Pembrolizumab	200 mg	Q3W	IV infusion	Day 1 of each 3 week cycle		

Drug Dose/Potency		Dose Frequency	Route of Administration	Regimen/Treatment Period		
Dietary Supplement	Amount	Frequency	Route	Consumption period		
EDP1503	>7.5x10 ¹⁰ CFU/capsule	2 capsules BID	Oral	Daily through the protocol study period		

5.2.1 Dose Selection/Modification

5.2.1.1 Dose Selection

The rationale for selection of doses to be used in this trial is provided in Section 4.0 – Background and Rationale.

Details on preparation and administration of pembrolizumab (MK-3475) are provided in the Pharmacy Manual.

5.2.1.2 Dose Modification (Escalation/Titration/Other)

Adverse events (both non-serious and serious) associated with pembrolizumab (or in combination with EDP1503) exposure may represent an immunologic etiology. These adverse events may occur shortly after the first dose or several months after the last dose of treatment. Pembrolizumab and EDP1503 must be withheld for drug-related toxicities and severe or life-threatening AEs. Supportive care guidelines, including use of corticosteroids are described below.

All Grade 3-5 adverse events considered possibly, probably or definitely related to study agent(s) must be discussed with the Lead Principal Investigator. All treating clinicians involved in the protocol are welcomed to discuss complicated cases at any time with the Lead Principal Investigator:

[name] University of Chicago Comprehensive Cancer Center [contact]

> Protocol Version: 04/10/2019 Page 21 of 72

Table 3 Dose Modification Guidelines (for both Pembrolizumab and EDP1503) for Drug-Related Adverse Events

Toxicity	Hold Treatment For Grade	Timing for Restarting Treatment	Treatment Discontinuation
Diarrhea/Colitis	2-3	Toxicity resolves to Grade 0-1	Toxicity does not resolve within 12 weeks of last dose or inability to reduce corticosteroid to 10 mg or less of prednisone or equivalent per day within 12 weeks
	4	Permanently discontinue	Permanently discontinue
AST, ALT, or	2	Toxicity resolves to Grade 0-1	Toxicity does not resolve within 12 weeks of last dose
Increased Bilirubin	3-4	Permanently discontinue (see exception below) ^a	Permanently discontinue
Type 1 diabetes mellitus (if new onset) or Hyperglycemia	T1DM or 3-4	Hold pembrolizumab for new onset Type 1 diabetes mellitus or Grade 3-4 hyperglycemia associated with evidence of beta cell failure	Resume pembrolizumab when patients are clinically and metabolically stable
Hypophysitis	2-4	Toxicity resolves to Grade 0-1. Therapy with pembrolizumab can be continued while endocrine replacement therapy is instituted	Toxicity does not resolve within 12 weeks of last dose or inability to reduce corticosteroid to 10 mg or less of prednisone or equivalent per day within 12 weeks
Hyperthyroidism	3	Toxicity resolves to Grade 0-1	Toxicity does not resolve within 12 weeks of last dose or inability to reduce corticosteroid to 10 mg or less of prednisone or equivalent per day within 12 weeks
	4	Permanently discontinue	Permanently discontinue

If a subject's study treatment has been interrupted for more than 2 doses of pembrolizumab, the investigator must contact the Lead Principal Investigator to review the subject's condition in order to resume the treatment.

If toxicities develop requiring treatment hold of pembrolizumab then EDP1503 supplement should be held as well. If toxicities not characteristic to pembrolizumab are present and the treating investigator believes the patient is deriving clinical benefit, pembrolizumab can be continued while holding EDP1503.

5.2.2 Timing of Dose Administration

All trial treatments and dietary supplements will be administered on an outpatient basis.

An initial EDP1503 administration period of two weeks in cohort 1 and one week in cohort 2 will precede dosing with pembrolizumab and will continue to be administered orally daily for the duration of the study. An exception to this for cohort 2 patients will include any patient who is among the first three patients enrolled who will have a 2 week run in to monitor for EDP1503 toxicities especially.

Pembrolizumab should be administered on Day 1 of each cycle after all procedures/assessments have been completed as detailed on the Trial Flow Chart (Section 6.0) and may be administered up to 3 days before or after the scheduled Day 1 of each cycle due to administrative reasons.

Pembrolizumab 200 mg will be administered as a 30 minute IV infusion every 3 weeks. Sites should make every effort to target infusion timing to be as close to 30 minutes as possible. However, given the variability of infusion pumps from site to site, a window of -5 minutes and +10 minutes is permitted (i.e., infusion time is 30 minutes: -5 min/+10 min).

The Pharmacy Manual contains specific instructions for the preparation of the pembrolizumab infusion fluid and administration of infusion solution. The Pharmacy Manual provides instruction for storage of EDP1503.

5.2.3 Trial Blinding/Masking

This is an open-label trial; therefore, the investigators and subject will know the treatment administered.

5.3 Randomization or Treatment Allocation

There is no randomization.

5.4 Stratification

There is no stratification.

5.5 Concomitant Medications/Vaccinations (allowed & prohibited)

Medications or vaccinations specifically prohibited in the exclusion criteria are not allowed during the ongoing trial. If there is a clinical indication for one of these or other medications or vaccinations specifically prohibited during the trial, discontinuation from trial therapy or vaccination may be required. The treating investigator should discuss any questions regarding this with the Lead Principal Investigator. The final decision on any supportive therapy or vaccination rests with the investigator and/or the subject's primary physician.

5.5.1 Acceptable Concomitant Medications

All treatments that the investigator considers necessary for a subject's welfare may be administered at the discretion of the treating investigator in keeping with the community standards of medical care. All concomitant medication will be recorded including all prescription, over-the-counter (OTC), herbal supplements, and IV medications and fluids. If changes occur during the trial period, documentation of drug dosage, frequency, route, and date may also be recorded.

5.5.2 Prohibited Concomitant Medications

Subjects are prohibited from receiving the following therapies during the Screening and Treatment Phase (including retreatment for post-complete response relapse) of this trial:

- Antineoplastic systemic chemotherapy or biological therapy
- Immunotherapy not specified in this protocol
- Chemotherapy not specified in this protocol
- Other dietary probiotics and prebiotics
- Investigational agents other than pembrolizumab
- Radiation therapy
 - o Note: Radiation therapy to a symptomatic solitary lesion or to the brain may be allowed after discussion between the investigator and Principal Investigator.
 - Live vaccines within 30 days prior to the first dose of trial treatment and while participating in the trial. Examples of live vaccines include, but are not limited to, the following: measles, mumps, rubella, varicella/zoster, yellow fever, rabies, BCG, and typhoid vaccine.
- Systemic glucocorticoids for any purpose other than to modulate symptoms from an event of clinical interest of suspected immunologic etiology. The use of physiologic doses of corticosteroids may be approved after consultation with the Lead Principal Investigator.
- Antibiotic therapies may be required by some participants during the study. EDP1503 should not be held during antibiotic therapy unless deemed necessary by the treating investigator. If there are continued gastrointestinal symptoms or the treating

investigator feels the subject is not fully recovered then the restart can be delayed for a maximum of 2 weeks.

Antibiotic choice: Different classes of antibiotics have been shown to disrupt the microbiome and potentially interfere with normal host immune function to varying degrees. If equally indicated amoxicillin is the preferred antibiotic as it minimally alters gut flora. Clindamycin is the most detrimental antibiotic and should be avoided if possible (Zaura et al 2015). Beta-lactams (other than amoxicillin) and fluoroquinolones broadly should be avoided if possible as well (Derosa et al 2017).

Citations

- Derosa et al 2017. Impact of antibiotics on outcome in patients with metastatic renal cell carcinoma treated with immune checkpoint inhibitors. Poster Abstract 462. J Clin Oncol 35, 2017

Subjects who, in the assessment by the treating investigator, require the use of any of the aforementioned treatments for clinical management should be removed from the trial or in the case of antibiotics the Bifidobacteria components of the study should be temporarily stopped. Subjects may receive other medications that the treating investigator deems to be medically necessary.

The Exclusion Criteria describes other medications which are prohibited in this trial.

There are no prohibited therapies during the Post-Treatment Follow-up Phase.

5.6 Rescue Medications & Supportive Care

5.6.1 Supportive Care Guidelines

Subjects should receive appropriate supportive care measures as deemed necessary by the treating investigator. Suggested supportive care measures for the management of adverse events with potential immunologic etiology are outlined below. Where appropriate, these guidelines include the use of oral or intravenous treatment with corticosteroids as well as additional anti-inflammatory agents if symptoms do not improve with administration of corticosteroids. Note that several courses of steroid tapering may be necessary as symptoms may worsen when the steroid dose is decreased. For each disorder, attempts should be made to rule out other causes such as metastatic disease or bacterial or viral infection, which might require additional supportive care. The treatment guidelines are intended to be applied when

the treating investigator determines the events to be related to pembrolizumab and/or EDP1503.

Note: if after the evaluation the event is determined not to be related, the investigator does not need to follow the treatment guidance (as outlined below). Refer to Section 5.2.1 for dose modification.

It may be necessary to perform conditional procedures such as bronchoscopy, endoscopy, or skin photography as part of evaluation of the event.

• Pneumonitis:

- For Grade 2 events, treat with systemic corticosteroids. When symptoms improve to Grade 1 or less, steroid taper should be started and continued over no less than 4 weeks.
- o For **Grade 3-4 events**, immediately treat with intravenous steroids. Administer additional anti-inflammatory measures, as needed.
- o Add prophylactic antibiotics for opportunistic infections in the case of prolonged steroid administration.

• Diarrhea/Colitis:

Subjects should be carefully monitored for signs and symptoms of enterocolitis (such as diarrhea, abdominal pain, blood or mucus in stool, with or without fever) and of bowel perforation (such as peritoneal signs and ileus).

- O All subjects who experience diarrhea/colitis should be advised to drink liberal quantities of clear fluids. If sufficient oral fluid intake is not feasible, fluid and electrolytes should be substituted via IV infusion. For Grade 2 or higher diarrhea, consider GI consultation and endoscopy to confirm or rule out colitis.
- o For **Grade 2 diarrhea/colitis**, that persists greater than 3 days, administer oral corticosteroids.
- For **Grade 3 or 4 diarrhea/colitis**, that persists > 1 week, treat with intravenous steroids followed by high dose oral steroids.
- When symptoms improve to Grade 1 or less, steroid taper should be started and continued over no less than 4 weeks.
- Type 1 diabetes mellitus (if new onset, including diabetic ketoacidosis [DKA]) or ≥ Grade 3 Hyperglycemia, if associated with ketosis (ketonuria) or metabolic acidosis (DKA)
 - o For **T1DM** or **Grade 3-4** Hyperglycemia
 - Insulin replacement therapy is recommended for Type I diabetes mellitus and for Grade 3-4 hyperglycemia associated with metabolic acidosis or ketonuria.
 - Evaluate patients with serum glucose and a metabolic panel, urine ketones, glycosylated hemoglobin, and C-peptide.

Protocol Version: 04/10/2019 Page 26 of 72

• Hypophysitis:

- For Grade 2 events, treat with corticosteroids. When symptoms improve to Grade 1 or less, steroid taper should be started and continued over no less than 4 weeks. Replacement of appropriate hormones may be required as the steroid dose is tapered.
- o For **Grade 3-4** events, treat with an initial dose of IV corticosteroids followed by oral corticosteroids. When symptoms improve to Grade 1 or less, steroid taper should be started and continued over no less than 4 weeks. Replacement of appropriate hormones may be required as the steroid dose is tapered.

Hyperthyroidism or Hypothyroidism:

Thyroid disorders can occur at any time during treatment. Monitor patients for changes in thyroid function (at the start of treatment, periodically during treatment, and as indicated based on clinical evaluation) and for clinical signs and symptoms of thyroid disorders.

- o Grade 2 hyperthyroidism events (and Grade 2-4 hypothyroidism):
 - In hyperthyroidism, non-selective beta-blockers (e.g. propranolol) are suggested as initial therapy.
 - In hypothyroidism, thyroid hormone replacement therapy, with levothyroxine or liothyroinine, is indicated per standard of care.

o Grade 3-4 hyperthyroidism

Treat with an initial dose of IV corticosteroid followed by oral corticosteroids. When symptoms improve to Grade 1 or less, steroid taper should be started and continued over no less than 4 weeks. Replacement of appropriate hormones may be required as the steroid dose is tapered.

Hepatic:

- o For **Grade 2** events, monitor liver function tests more frequently until returned to baseline values (consider weekly).
 - Treat with IV or oral corticosteroids
- o For **Grade 3-4** events, treat with intravenous corticosteroids for 24 to 48 hours.
- O When symptoms improve to Grade 1 or less, a steroid taper should be started and continued over no less than 4 weeks.

• Renal Failure or Nephritis:

- o For **Grade 2** events, treat with corticosteroids.
- o For **Grade 3-4** events, treat with systemic corticosteroids.
- O When symptoms improve to Grade 1 or less, steroid taper should be started and continued over no less than 4 weeks.

Protocol Version: 04/10/2019 Page 27 of 72 • Management of Infusion Reactions: Signs and symptoms usually develop during or shortly after drug infusion and generally resolve completely within 24 hours of completion of infusion.

Table 3 below shows treatment guidelines for subjects who experience an infusion reaction associated with administration of pembrolizumab.

Table 3 Infusion Reaction Treatment Guidelines

NCI CTCAE Grade	Treatment	Premedication at subsequent dosing
Grade 1 Mild reaction; infusion interruption not indicated; intervention not indicated	Increase monitoring of vital signs as medically indicated until the subject is deemed medically stable in the opinion of the investigator.	None
Grade 2 Requires infusion interruption but responds promptly to symptomatic treatment (e.g., antihistamines, NSAIDS, narcotics, IV fluids); prophylactic medications indicated for <=24 hrs	Stop Infusion and monitor symptoms. Additional appropriate medical therapy may include but is not limited to: IV fluids Antihistamines NSAIDS Acetaminophen Narcotics Increase monitoring of vital signs as medically indicated until the subject is deemed medically stable in the opinion of the investigator. If symptoms resolve within one hour of stopping drug infusion, the infusion may be restarted at 50% of the original infusion rate (e.g., from 100 mL/hr to 50 mL/hr). Otherwise dosing will be held until symptoms resolve and the subject should be premedicated for the next scheduled dose. Subjects who develop Grade 2 toxicity despite adequate premedication should be permanently discontinued from further trial treatment administration.	Subject may be premedicated 1.5h (± 30 minutes) prior to infusion of pembrolizumab (MK-3475) with: Diphenhydramine 50 mg po (or equivalent dose of antihistamine). Acetaminophen 500-1000 mg po (or equivalent dose of antipyretic).
Grade 3: Prolonged (i.e., not rapidly responsive to symptomatic medication and/or brief interruption of infusion); recurrence of symptoms following initial improvement; hospitalization indicated for other clinical sequelae (e.g., renal impairment, pulmonary infiltrates) Grade 4: Life-threatening; pressor or ventilatory support indicated	Stop Infusion. Additional appropriate medical therapy may include but is not limited to: IV fluids Antihistamines NSAIDS Acetaminophen Narcotics Oxygen Pressors Corticosteroids Epinephrine Increase monitoring of vital signs as medically indicated until the subject is deemed medically stable in the opinion of the investigator. Hospitalization may be indicated. Subject is permanently discontinued from further trial treatment administration.	No subsequent dosing

• Management of Stevens-Johnson syndrome and Toxic Epidermal Necrolysis:

To date, approximately 11,000 patients in clinical trials and 27,000 patients in the post-marketing setting have been treated with KEYTRUDA®. One fatal case of SJS in a clinical trial and one fatal case of TEN in the post-marketing setting have been reported in patients treated with KEYTRUDA®. Including these cases, there have been 8 cases of SJS (6 in clinical trials, and 2 post-marketing) and 2 cases of TEN (both post-marketing) all of which were serious.

- o For signs or symptoms of SJS or TEN, withhold KEYTRUDA® and refer the patient for specialized care for assessment and treatment.
- o If SJS or TEN is confirmed, permanently discontinue KEYTRUDA®.

Management of Immune-mediated myocarditis:

A total of 6 cases of myocarditis have been reported in patients treated with KEYTRUDA® in clinical trials or in an expanded access program. There was 1 fatal case reported in a clinical trial.

o For suspected immune-mediated myocarditis, ensure adequate evaluation to exclude other etiologies, and administer corticosteroids as appropriate.

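### Section 5.6.1 suggests steroids later for Grade 3 or 4 diarrhea/colitis (after more than 1 week) than for Grade 2 (after more than 3 days)

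*Combined protocol and SAP*

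**What the plan says.** The diarrhea/colitis entry in section 5.6.1 has two adjacent steroid bullets. The first covers Grade 2 and sets this trigger and regimen: "that persists greater than 3 days, administer oral corticosteroids". The second covers both higher grades, with a longer wait and a stronger regimen: "that persists > 1 week, treat with intravenous steroids followed by high dose oral steroids".

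The section gives these as advice: "Suggested supportive care measures for the management of adverse events with potential immunologic etiology are outlined below". It also says: "Subjects should receive appropriate supportive care measures as deemed necessary by the treating investigator". The guidance applies once the treating investigator has judged the event related to pembrolizumab or EDP1503.

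Other Grade 3-4 steroid rules in the section are worded differently. For pneumonitis: "immediately treat with intravenous steroids". For hypophysitis: "treat with an initial dose of IV corticosteroids followed by oral corticosteroids". For hyperthyroidism: "Treat with an initial dose of IV corticosteroid followed by oral corticosteroids". The hepatic and renal entries also go straight to steroids at Grade 3-4.

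No other section of the protocol or SAP sets a steroid start time for Grade 3-4 diarrhea/colitis.

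**The concern.** A severity-graded guideline would be expected to act at least as early at the higher grade. Here the wait more than doubles, from 3 days to 7, as the grade rises from 2 to 3 or 4. The same entry asks sites to watch for enterocolitis and bowel perforation.

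This bullet is the only written steroid prompt for Grade 3-4 colitis, and section 10.2 says the study will run in private practices as well as academic centers. A clinician who follows it literally would have no written prompt to start steroids in the first week of a Grade 3 or 4 event. What is at stake is patient safety. The primary endpoints, decision rules, sample size and planned analyses do not depend on this text.

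**Working it through.** The plan states no figure for this point, so there is none to reproduce. The check is a day count and a comparison of rules.

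**Inputs.** Both thresholds are from section 5.6.1: Grade 2, more than 3 days; Grade 3 or 4, more than 1 week (7 days). Onset is counted as day 1. A condition of more than k days is first met on day k + 1.

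**Event at one grade from onset.**
- Grade 2: 3 + 1 = day 4.
- Grade 3 or 4: 7 + 1 = day 8.
- Difference: 8 − 4 = 4 days.

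**Patient who worsens from Grade 2 to Grade 3 on day 3.** The bullet does not say whether the clock restarts when the grade changes. Section 8.2.4 speaks of grade changing within a single episode, so both readings are open.
- Counted from onset of the episode: day 8, and 8 − 4 = 4 days after a patient who stayed at Grade 2.
- Counted from worsening: days 3 to 9 make 7 days, so the condition is first met on day 10, and 10 − 4 = 6 days after.
- Range: 4 to 6 days. The order is inverted on either reading.

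**Comparison within section 5.6.1.**

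| Entry | Grade 2 steroid rule | Grade 3-4 steroid rule |
|---|---|---|
| Pneumonitis | no wait | no wait (immediate) |
| Hypophysitis | no wait | no wait |
| Hyperthyroidism | none (beta-blocker) | no wait |
| Hepatic | no wait | no wait |
| Renal failure or nephritis | no wait | no wait |
| Diarrhea/colitis | more than 3 days | more than 1 week |

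The 24 to 48 hours in the hepatic entry is a length of treatment, not a delay. Infusion reactions (corticosteroids listed as one option) and myocarditis (not graded) are left out of the count; neither has a wait. So 1 of 6 graded Grade 3-4 steroid rules carries a wait. Diarrhea/colitis is also the only entry whose Grade 2 steroid rule carries one.

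**Would a shorter wait do?** Try more than 3 days at Grade 3 or 4 for the patient who worsens on day 3.
- Counted from onset of the episode: day 4, the same as Grade 2. The inversion is gone.
- Counted from worsening: days 3 to 5 make 3 days, first met on day 6, and 6 − 4 = 2 days late. The inversion returns.

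A shorter wait therefore works only if the clock is tied to onset of the episode.

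**The case against.** The strongest reply is that nothing here holds treatment back. Section 5.5 leaves the final decision on supportive therapy to the investigator or the patient's primary physician. Section 5.5.1 allows any treatment considered necessary for the patient's welfare. Section 5.5.2 exempts steroids for suspected immune-related events of clinical interest from its ban. Several measures carry no wait:
- Drug hold at Grade 2-3 and permanent discontinuation at Grade 4 (section 5.2.1.2, dose modification table).
- Fluids and monitoring for perforation (section 5.6.1).
- Specialist work-up: "For Grade 2 or higher diarrhea, consider GI consultation and endoscopy to confirm or rule out colitis".
- Reporting of serious adverse events to the Lead Principal Investigator within 24 hours of site knowledge (sections 8.2.3.1 and 8.2.5). Table 6 defines Grade 3 partly by an indication for hospitalization, so few such events may escape this, although a Grade 3 event managed as an outpatient is not automatically covered.

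All of this stands and limits the hazard. None of it sets a steroid start time, and freedom to depart from a prompt does not put the prompt in the right order.

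A second reply is that diarrhea differs from the other entries. Loose stool is a listed minor effect of Bifidobacterium foods (section 4.2.2), infection has to be considered, and the protocol already uses persistence at Grade 2. This stands in part: the lack of a wait in the other entries does not prove that no wait is right for colitis. But section 5.6.1 asks for other causes to be ruled out for every disorder, and the guidance applies only after the event is judged related. Neither consideration supports a longer wait at the higher grade.

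A reader might also infer more than the documents support:
- *That steroids are withheld for a week.* Earlier use is permitted, so the day counts are gaps between written prompts, not treatment delays.
- *That the two waits were swapped by mistake.* The documents do not show whether the order was intended, and the bullets prescribe different regimens.
- *That the rule contradicts Table 6, which calls for urgent intervention at Grade 4.* Table 6 names no steroid. The two fit poorly together but do not directly conflict.

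**Conclusion.** The concern holds as a limited patient-safety point. The inversion is certain from two adjacent bullets, and nothing elsewhere corrects it. Its size is 4 days for an event at one grade from onset, and 4 to 6 days for the example of worsening on day 3. Quoting 6 days alone would assume that the clock restarts when the grade changes, which the text does not say.

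These figures assume that onset is day 1 and that the bullets are followed literally. The documents give no expected number of Grade 3-4 colitis events, so the number of patients affected cannot be estimated. The wording should be fixed because the change is cheap and no argument in the documents supports a later prompt for the more severe event.

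**What to change.** In section 5.6.1, delete the one-week persistence condition from the Grade 3 or 4 diarrhea/colitis bullet. Grade 3 or 4 diarrhea/colitis judged related would then be treated with intravenous and then high-dose oral steroids without a set wait. Add one sentence: a patient who worsens to Grade 3 or 4 follows this rule at once.

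The earliest possible prompt then becomes day 1 for an event that starts at Grade 3 or 4, and day 3 for the patient who worsens on day 3. In practice it falls when the investigator judges the event related. Investigator discretion is unchanged.

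If the clinical team prefers to keep a persistence condition, it should be no later than the Grade 2 trigger, and the text should say that it is counted from onset of the episode. The exact timing within that limit is a clinical decision.

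The cost is a short wording amendment. Under section 12.6 it needs University of Chicago IRB approval, then approval by each affiliate's IRB within 3 months of receipt. Sample size, visits and analysis do not change.
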